5 INVESTIGATIONAL PLAN

5.1 Overall clinical trial design

This clinical trial will be conducted as a multicentre, open label clinical trial involving male or female subjects of any race, aged ≥ 18 years with clinically confirmed thin or non-hyperkeratotic and non-pigmented multiple AKs in an anatomical area on the face or scalp , and meeting other specific eligibility criteria.

A total of 50 subjects will be enrolled in approximately 8 sites in Germany. Approximately 5 to 10 subjects are planned for each site.

At baseline subject eligibility will be validated and the anatomical area to be treated on the face (e.g., forehead or cheek or chin) excluding nose, eyelids, lips and mucosa, or balding scalp, will be selected by the investigator.

Subjects will receive from the investigator adequate training and detailed instructions about Luxerm® treatment. Eligible subjects will apply the Luxerm® treatment with daylight PDT within 1 week (\pm 7 days) to the baseline visit depending on appropriate weather conditions to allow daylight exposure.

Subjects will be evaluated up to three times during the study; at baseline, Day 1 post-treatment (\pm 2 days) and week 12 post treatment (\pm 7 days).

5.2 Discussion of clinical trial design

Luxerm® is registered in Germany; this study is therefore considered as Phase IV. Luxerm® cream is a topical therapy currently approved for treatment of thin or non-hyperkeratotic and non-pigmented actinic keratoses (AKs) on the face and scalp. In several clinical trials it has been shown to be highly effective, safe, well-tolerated and to give excellent cosmetic outcomes with minimal risk of scarring.

An interventional design is applied in this study because it allows assessment of patient reported outcomes to Luxerm® treatment satisfaction in addition to safety and efficacy evaluations of Luxerm® daylight photodynamic therapy as per local SmPC. Information on the treatment application will be recorded by the subject in a questionnaire and reported in an electronic Case Report Form (eCRF).

Although several studies have already been conducted with MAL DL-PDT to treat different skin conditions, it is felt that a clinical trial is required to confirm the subject reported outcomes with DL-PDT to assess the level of satisfaction.

5.3 Clinical trial duration and termination

The average planned period for the clinical trial from First Subject In (FSI) to Last Subject Out (LSO) is 6 months. The end date of the clinical trial will be the date of the last visit of the last subject who participates in the clinical trial.

The planned duration of recruitment (i.e. From FSI to Last Subject In (LSI)) is approximately 3 months.

The clinical trial may be terminated by the investigator at his/her clinical trial site at any time with appropriate notification to *GALDERMA R&D*. Likewise, *GALDERMA R&D* may terminate the clinical trial and/or the participation of the clinical trial site(s) with appropriate notification.

The expected duration of subject participation is approximately 15 weeks.

5.4 Clinical trial flow chart

STUDY PROCEDURES	Baseline Visit 1 D0	Treatment Day ^g (at patient's home)	Day 1 post- treatment Visit 2 (± 2 days)	Week 12 post- treatment Visit 3 (± 7 day)
Informed consent	X			
Inclusion/Exclusion criteria	X			
Demography/Medical history	X			
Previous therapies ^a	X			
Urine pregnancy test ^d	X			X ^e
Concomitant therapies	X		X	X ^e
Lesion mapping and counting ^c	X			X ^e
Sunscreen application		X		
Skin preparation	X ^k	X ⁱ		
Luxerm® application and DL treatment session		X		
Lesion response using the transparent plastic sheet (for initial treated AK lesions)				X ^e
Clinical assessment of skin aspect for AK lesions in complete response				X ^e
Count of new AK lesions using the transparent plastic sheet				X
Photodamage Dovers assessment	X			X ^e
Adverse events ^b (including local skin reaction)	X		X	X ^e
Subject questionnaire		X ^f		X ^e
Physician questionnaire ^j				X ^e
Photographs ^h	X			X ^e
Treatment Dispensed	X			
Subject Compliance			X	
Study treatment return			X	
Exit form				X ^e

- a. Treatment that continues after visit 1 should be recorded on the concomitant therapies form of the CRF.
- b. Adverse Events have to be collected from the moment the Informed Consent signature is obtained and recorded on the AE form of the CRF.
- c. Actinic keratosis lesions in the treated area will be counted. For accurate counting, lesion localization and follow-up, a clear plastic sheet will be placed over the anatomical area of the face or scalp being treated and other anatomical landmarks will also be marked on this sheet
- d. For subject of childbearing potential: The determination of UPT is mandatory at baseline and at week 12 or before if there is early termination. UPT must have a sensitivity of less than at least 25IU/L. In case of positive UPT during the study the investigator will withdraw the subject from the clinical trial according to the procedure for reporting pregnancy details in the protocol.
- e. To be performed at week 12 or before in case of early termination.

- f. After the 2 hours daylight exposure.
- g. Subject advised to ensure the treatment as close as possible to the baseline visit (within 1 week (\pm 7 days)) and with appropriate weather conditions, to ensure the treatment instructions are followed. At 1 week post-baseline, if the investigator has not heard from subject, he will call the subject to check if the study treatment has been performed (see [section 4.4](#)). Subject instructs to call the investigator to confirm the treatment has been well completed and to schedule the day 1 post-treatment visit.
- h. At selected sites and for subjects who have signed a photograph release informed consent form.
- i. Using the skin pad as per investigator instructions.
- j. To be completed once all subjects from the site have completed the study
- k. Removal of any scales and crusts in the anatomical area by the investigator if deemed necessary

5.5 Clinical trial visit description and procedures

5.5.1 Visit 1 - Baseline visit

- 1. Explain the nature and the constraints of the clinical trial to the subject particularly the study treatment instructions.
- 2. Have the subject read, understand, date and sign an approved informed consent form (ICF). Give a dated and signed copy to the subject.
- 3. Perform a urine pregnancy test (UPT) for female subjects of childbearing potential.
- 4. If subject female of childbearing potential agrees to participate to the clinical trial, make sure she is using the requiring method(s) of contraception (see inclusion criteria [4.2.1](#)). Make sure that the urine pregnancy test is done and the result is negative before subject inclusion in the trial
- 5. Check inclusion/exclusion criteria (see sections [4.2.1](#) and [4.2.2](#)).
- 6. Log into the electronic case report form (eCRF) to get a Subject Identification Number.
- 7. Question the subject about demography, relevant medical history, prior and concomitant therapies.
- 8. Inform the subject about authorized and prohibited concomitant therapies. If the subject requires a medication washout period, the subject's baseline evaluation must be conducted after the washout period has been completed.
- 9. Select the subject's anatomical area on the face (e.g., forehead or cheek or chin) excluding nose, eyelids, lips and mucosa, or balding scalp to be treated according to inclusion criteria 2 (see [4.2.1](#))
- 10. Map the selected anatomical area on the transparent plastic sheet and mark and count the AK lesions
 - a) Delimit clearly the anatomical area on a transparent plastic sheet using a permanent marker to ensure clinical assessments are always done on the exact same area (indicate some reference to "landscape markers" such as: eyebrows, nose, ears, joints, nevus, etc.) and draw the clinical margins of each AK lesion.

- b) Circle and mark each AK lesion of the anatomical area on the transparent plastic sheet.
- c) Record the total number of AK lesions presents in the anatomical area in the CRF.
- d) If necessary, scales and crusts should be carefully removed on the treated areas of the face and/or balding scalp.

11. If the subject is eligible, dispense the study treatment (see specific section 6.1.2):

- a) Fill in a prescription form.
- b) Dispense to the subject the investigational product according to the prescription form
- c) Affix the tear-off portion of the label on the product dispensation log and report the required information on the labels if applicable.
- d) Provide appropriate verbal and written instructions on how to properly use the investigational product(s) and how to perform the treatment procedure (see instruction in section 6.1.4)
- e) Emphasize the importance of complying with the given instructions and treatment; instruct the subject to bring back the dispensed investigational product(s) at the next visit.

12. Dispense to the subject any associated non-investigational product(s).

13. Give and provide instruction to the subject how to use the provided Moisturizer in case some tolerability reactions occur (see 0).

14. Remind the Subject to avoid sun exposure of the treated anatomical area and the use of sunscreen for about 2 days following treatment procedures.

15. Assess the skin photodamage of the selected anatomical area using the Dover's modified global photodamage score (see 7.4.1).

16. Provide guidance on the satisfaction questionnaire (see appendix 1) and ask the subject to fill it out the day of treatment after the daylight exposure. Remind the subject to return it at the next study visit (Day 1 post-treatment).

17. *For selected sites only*, take photographs of the target anatomical area according to the provided procedure only if subject has agreed on the approved photo release consent form.

18. For all female subjects of childbearing potential, emphasize the guidelines about contraception and risks in case of pregnancy.

19. Instruct the subject to call you the day of treatment to confirm the treatment has been well completed and to schedule the next study visit (Day 1 post-treatment). **If you have not heard of subject one week after the baseline, contact him/her to get news and refer to section 4.4.**

At a minimum, tasks numbered 9, 10 and 15 have to be performed by a Dermatologist.

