Short title (± acronym): SESAME 2		
Project number: 834	Clinical trial phase: Phase IV	Clinical trial period Planned First Subject In: May 2017 Planned Last Subject Out: Nov. 2017
Investigational product:		
Name:	Luxerm®	
Pharmaceutical form:	Cream	
Dose/concentration:	160mg/g of methyl aminolevulinate	
Total daily dose:	One application	
Mode and frequency of administration:	
One session of Luxerm® daylight photodynamic therapy: a sunscreen with chemical filters will be applied to all sun exposed areas including the treatment area to prevent subsequent UVA and UVB exposure (as provided for the study). After the sunscreen has dried, the selected anatomical area should be prepared to facilitate access of the cream and light to all lesions. An abrasive pad should be used to roughen the affected area. Following skin preparation, a thin layer of Luxerm® cream should be applied on the anatomical area (field application), without occlusion.
 
After Luxerm® application, subject will go outdoor under direct daylight no later than 30 minutes. On sunny days, should the subject feel uncomfortable in direct sunlight, shelter in the shade may be taken.
 
After 2-hour of daylight exposure, subjects will return indoors and Luxerm® will be removed.
 
Subjects will be instructed to avoid sun exposure and use sunscreen for the next 48 hours.
 
The subject will be assessed at baseline and day 1 post-treatment as well as at week 12 post-treatment.
	
Location of treated area:	Face or scalp	
Duration of treatment:	One day	
Comparator product:	Not applicable	
Non-investigational product to be provided for the clinical trial:	
 • Urine Pregnancy Test • Actinica sunscreen SPF 50+ on all exposed areas. • Cetaphil moisturizer cream at night for 8 days on the treated area after Luxerm DL-PDT • Skin abrasive pad for skin preparation on the anatomical area 	

Clinical trial title:		
Subject reported outcomes on satisfaction, efficacy and safety with Luxerm® in the field-directed treatment of thin or non-hyperkeratotic and non-pigmented Actinic Keratosis of the face or the scalp		
Short title (± acronym): SESAME 2		
Project number: 834	Clinical trial phase: Phase IV	Clinical trial period Planned First Subject In: May 2017 Planned Last Subject Out: Nov. 2017

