4.3.3 Recording

Previous and concomitant therapies will be recorded on the Drugs/Therapies Form (for drugs/therapies) and/or on the Medical and Surgical Procedures form (for medical/surgical procedures) in the case report form (CRF).

Concomitant therapies will be recorded, reviewed, and updated at each trial visit.

Every attempt should be made to keep concomitant therapy dosing and regimen constant during the study. Any change to the concomitant therapy should be noted on the CRF. Any new concomitant therapy or modification of an existing therapy may be linked to an adverse event (AE). A corresponding Adverse Event Form must be completed to account for the change in therapy, except in some cases such as therapy used for prophylaxis, dose modification for a chronic condition, etc.

4.3.4 Authorised therapies during the clinical trial.

Unless listed in the exclusion criteria above or in the prohibited therapies (see sections [4.2.2](#) and [4.3.5](#)), all therapies are authorised.

Subject may use the sunscreen and moisturizer provided for the trial as required for the symptomatic relief of skin dryness or irritation (use of moisturizer other than the provided one will be captured in the CRF as concomitant therapy).

Note: It is preferred that a moisturizer (provided one or a one not containing alpha hydroxy acid) be added to the treatment regimen as opposed to implementing an altered dosage regimen.

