4.3.5 Prohibited therapies during the clinical trial

The following therapies are prohibited because they may interfere with the efficacy and/or safety assessment of the investigational product, or because they may interact with the metabolism of the investigational product:

- On the anatomical area, all topical treatment, medical/surgical procedures listed as exclusion criteria (section [4.2.2](#)).
- All systemic therapies listed in exclusion criteria (section [4.2.2](#)).
- Any other drugs/procedures which in the investigator's judgment are liable to interfere or interact with the efficacy or safety of Luxerm®.
- Any UV-therapy should be discontinued before treatment.

- As a general precaution, sun exposure of the treated anatomical area should be avoided for about 2 days following treatment
- If any outdoor sun exposure the subject will be recommended to apply the provided sunscreen.
- Any treatment including cryotherapy is prohibited except at the end of the study to treat AK lesions at last visit after study clinical assessments.
- If subject presents mild/moderate/severe AKs outside anatomical area and investigator wishes not to wait the end of study before treating them, he/she can do so but in this case only cryotherapy can be used. In order to avoid interference with subject pain assessment, it should be done once all study assessments, including subject questionnaire completion, have been performed at the baseline visit.

If prohibited therapies become a necessary treatment for the safety or best interest of the subject, *GALDERMA R&D* will be notified to discuss possible alternatives prior to administration of a prohibited therapy and to discuss the pertinence and the modalities for the subject to continue in the clinical trial.

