5.6 Subject instructions

At baseline, subject will be requested to comply with the treatment procedure instructions. After having trained the subject, the investigator will provide him/her with the written study treatment instruction sheet including storage conditions.

Throughout the study, Subject will be requested to comply with the following:

1. To avoid the use of antalgics the day of treatment and the day before treatment until the subject self-assessment of pain is complete.
2. To avoid Sun exposure of treated anatomical area and use sunscreen during the 2 days following the treatment.
3. To apply a moisturizer in case signs of local skin irritation such as dryness or erythema are observed after the PDT procedure. The subject will be instructed that the use of a moisturizer should be considered only after the study treatment and when self-assessment of pain is performed.
4. To respect the visit timeframe.
5. In case the subject is using forbidden topical therapy listed in exclusion criterion (Section [4.2.2](#)) or any other treatment on an area other than the anatomical area, the Investigator will remind him/her to pay a strict attention to not apply any of these therapies on the anatomical area.

Please refer to Section 4.2.1 and Section 4.2.2 for other items linked to eligibility criteria.

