6.1.4 Instructions for use and administration

At baseline visit the investigator or designee will give each subject verbal and written instructions on how to use the investigational and non-investigational products. It will be confirmed to treat the selected AKs anatomical area on the face excluding nose (e.g., forehead or cheek or chin), or balding scalp (excluding eyelids, lips and mucosa) with field therapy by providing the subject with the study treatment and by explaining in details the procedure.

Table 2: Procedures for Luxerm® DL-PDT treatment

Baseline Visit 1	Anatomical area and lesion mapping by the investigator using a transparent plastic sheet (after confirmation that all inclusion criteria and none of the exclusion criteria are met). Removal of any scales and crusts in the anatomical area by the investigator if deemed necessary.	
	Subject provided with oral and written instructions on the treatment procedure of the anatomical area (lesions and field). The patient should undergo treatment at home in the following week (\pm 7 days), with appropriate weather conditions, as follow:	
Treatment day*	t -15 min	The subject applies Actinica sunscreen on the selected anatomical area and all other sun exposed skin. The quantity of sunscreen will be sufficient to cover all areas exposed during the DL exposure step.
	t=0 min	After approximately 15 min once the sunscreen (Actinica sunscreen) has dried, the subject prepares the anatomical area to be treated with an abrasive pad to remove scales and crusts and roughen the surface of the lesions
	t=30 min	Then, the subject applies a thin layer of Luxerm® on the entire anatomical area using the provided finger glove and avoiding contact with eyes, lips and mucous membranes.
	t=2h30	The subject goes outdoors no later than 30mins of application of Luxerm® for 2 hours daylight exposure. On sunny days, should the subject feel uncomfortable in direct sunlight, shelter in the shade may be taken.
		The subject returns indoors and Luxerm® is removed by washing

* Subject will be advised to follow the instructions as close to the baseline visit (within 1 week \pm 7 days) with appropriate weather condition to ensure the instructions are well followed.

As a general precaution, sun exposure of the treated anatomical area should be avoided for about 2 days following treatment. Subjects are advised to use a sunscreen in all exposed areas, including the treated area, during this period

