6.2 Other supplies

Galderma will provide the sites with:

- The Urinary Pregnancy Tests (UPT) that may detect urinary Human Chorionic Gonadotropin concentrations equal to or greater than 25 international unit)
- Cetaphil moisturizer cream
- Actinica Sunscreen SPF 50+
- Nitril finger gloves for Luxerm® cream application
- An abrasive pad for skin preparation
- Cool bag for Luxerm® cream transportation

No specific labels will be used.

No accountability will be conducted on these products.

The provided sunscreen has been selected so as not to prevent the transmission of light wavelengths required for activation of PpIX and to offer an adequate sun protection for the 2-hour duration of the DL exposure. The provided sunscreen will be used only for the treatment preparation and will be applied if any sun exposure is expected following the treatment.

Cetaphil moisturizer cream will be used on the whole anatomical area at night for 8 days after treatment. It is provided in case of occurrence of phototoxicity reaction on the anatomical area treated (burning sensation, prickling or tingling skin, irritation such as dryness, redness, edema or crusts) after the daylight exposure or soon after, requiring the use of moisturizer. **Moisturizer application should not be done before the treatment procedure or before the Subject Self-assessment of Pain is completed.**

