7.3.1 Adverse Events

Adverse events (AEs) are to be monitored throughout the course of the clinical trial.

All AEs including local skin reactions are to be reported on an Adverse Event Form of the eCRF with complete information as required. If AEs occur, the main concern will be the safety of the subject. At the time of the ICF signature, each subject must be provided with the name and telephone number of clinical trial center personnel for reporting AEs and medical emergencies.

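### Section 5.5.1 item 14 reads as telling subjects to avoid sunscreen for about 2 days after treatment, while the synopsis, 5.6 and 6.1.4 tell them to use it

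*Combined protocol and SAP*

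**What the plan says.** Seven places in the protocol deal with sunscreen after the treatment session.

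- **Section 5.5.1, item 14** (investigator task at baseline): "Remind the Subject to avoid sun exposure of the treated anatomical area and the use of sunscreen for about 2 days following treatment procedures".
- **Synopsis**, mode of administration: "Subjects will be instructed to avoid sun exposure and use sunscreen for the next 48 hours".
- **Section 5.6, item 2** (subject instructions): "To avoid Sun exposure of treated anatomical area and use sunscreen during the 2 days following the treatment".
- **Section 6.1.4**, below Table 2, referring to the roughly 2 days after treatment: "Subjects are advised to use a sunscreen in all exposed areas, including the treated area, during this period".
- **Section 4.3.5**: "If any outdoor sun exposure the subject will be recommended to apply the provided sunscreen".
- **Section 6.2**: "The provided sunscreen will be used only for the treatment preparation and will be applied if any sun exposure is expected following the treatment".
- **Section 4.3.4**: "Subject may use the sunscreen and moisturizer provided for the trial as required for the symptomatic relief of skin dryness or irritation".

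Section 7.3.1 adds that "All AEs including local skin reactions are to be reported on an Adverse Event Form of the eCRF with complete information as required", and section 9.1.1.2 lists incidence and severity of adverse events as a safety variable.

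**The concern.** Item 14 is a numbered step that the investigator carries out, not background text. Taken literally, it passes on the reverse of what three other places say for the same days. The subject treats at home, and baseline is the only scheduled visit before that. The Visit 2 tasks in section 5.5.2 include no sunscreen reminder. With a window of day 1 ± 2 days, that visit can also fall on day 3, after the 2-day period is over.

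Two things are at stake. The first is subject protection: a subject could be told to leave sunscreen off when the rest of the protocol says to apply it. The second is uniform conduct: with about 8 sites and 5 to 10 subjects at each, different sites could pass on different instructions. The planned records would not readily show this. Appendix 1 question 4 asks about sunscreen for the daylight session only, and section 6.2 keeps no accountability for the product. Section 4.3.2 does list sunscreens among the therapies to be recorded, so some later use may be captured. No listed item asks which instruction the subject received or followed.

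**Working it through.** The plan gives no figure on this point and none can be derived, so the check is a comparison of text.

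**Step 1: how item 14 can be read.** The verb *avoid* is followed by two objects joined by *and*: sun exposure, and the use of sunscreen. Read as written, both are to be avoided. The other reading, that the subject is reminded to avoid sun and is also reminded of using sunscreen, needs a word that is not there. The synopsis and 5.6 item 2 have nearly the same sentence with a separate verb for sunscreen. That is why a dropped verb is the likely explanation.

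**Step 2: what each place tells a subject in the 2 days after treatment.**

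| Place | Subject goes out in the sun | Subject stays out of the sun |
|---|---|---|
| 5.5.1 item 14, as written | Do not use | Do not use |
| Synopsis | Use | Use (no condition stated) |
| 5.6 item 2 | Use | Use (no condition stated) |
| 6.1.4 | Use, treated area included | Unclear: depends on what counts as an exposed area |
| 4.3.5 | Recommended | Not triggered |
| 6.2 | Use if exposure is expected | Not triggered |
| 4.3.4 | Permitted for dryness or irritation | Permitted for dryness or irritation |

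**Step 3: what the table shows.** For a subject who goes out in the sun, item 14 is the only entry that says not to use sunscreen. The synopsis, 5.6, 6.1.4, 4.3.5 and 6.2 all point to using it, and 4.3.4 is permissive. For a subject who stays out of the sun, the synopsis and 5.6 differ from 4.3.5 and 6.2, but only over whether sunscreen is still called for. Section 4.3.4 introduces a third trigger, symptoms, in a sentence that covers sunscreen and moisturizer together.

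**Step 4: does 6.2 forbid later use?** No. The restriction to treatment preparation is followed in the same sentence by use after treatment when sun exposure is expected.

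**Step 5: is there a stated route to the results?** Local skin reactions are recorded as adverse events, so a formal path exists. However, the phototoxic reactions described in 6.2 are tied to the daylight session or soon after it. Sunscreen before that session is stated consistently in the synopsis, Table 2 and Appendix 1. No section links sunscreen use on later days to adverse event rates, to bother from side effects or to days of social embarrassment. The pain score is taken straight after the session, so it is not involved.

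**The case against.** The strongest reply is that investigators would not be misled. Item 14 is only a reminder. At the same visit, item 11d requires verbal and written instructions and refers to 6.1.4, which says to use sunscreen, and item 12 dispenses the non-investigational products, which include it. Every place that covers the 2-day period also says to avoid sun exposure, so that part of the protection is consistent. Subjects receive a written sheet (5.6) and sites a reference manual (10.1), either of which may be clear.

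Most of this stands, and it makes a drafting slip the best explanation. It does not remove the point. Item 14 still contradicts the section that item 11d refers to, and the sheet and manual are not in the documents, so they cannot be assumed to settle the matter.

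A reader might infer three stronger things that the documents do not support:

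- *That there are three mutually opposed instructions.* Only item 14 is opposite. The other differences are in trigger, and they overlap.
- *That the safety and questionnaire results would reflect which instruction a site gave.* Step 5 finds no such link and no size for one.
- *That all 50 subjects would be affected.* This would require every site to adopt the literal reading, with no correction from 6.1.4, the sheet, the manual or training.

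**Conclusion.** The inconsistency is real and worth correcting, and it is limited in reach. One operative instruction, 5.5.1 item 14, contradicts the synopsis, 5.6 item 2 and 6.1.4 as written. Sections 4.3.4, 4.3.5 and 6.2 add different triggers without being opposite.

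The number of subjects who might receive the contrary message lies between 0 and the planned 50, and the documents give no basis for a narrower range. The trial has one arm and section 9.1.4 rules out inferential statistics, so no test, sample size, population or endpoint definition is affected.

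The conclusion assumes that investigators may work from item 14 as printed and that the subject sheet, which cannot be seen here, does not already resolve it. Calling item 14 a probable slip is a judgement on the text alone, not a view on which sunscreen rule is clinically right.

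**What to change.** Reword item 14 of section 5.5.1 so that it can be read in only one way. Reconcile it with the synopsis and sections 4.3.4, 4.3.5, 5.6 item 2, 6.1.4 and 6.2, with one identical statement of whether, when and on which skin sunscreen is used after treatment. Check the written subject instruction sheet and the site reference manual against that statement. The sponsor's medical team decides the content.

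The cost is wording edits in up to seven places and a check of two site documents. If the protocol is already approved, the sponsor must judge whether the edits need an amendment under section 11.1. There is no cost to data collection or analysis.
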